Appendix 11 – Guideline for Fever Management

APPENDIX 12

THROMBOEMBOLIC EVENTS GUIDELINE

Guideline for thromboembolic events during the full plasma exchange (FPE)

A) Suspicion of venous thrombosis related to the catheter

- 1- In case of cervical pain, neck or superior limb edema, odynophagia or pulsating cephalgia, the caregiver will call the Investigator and will go to a nearby Emergency Room (ER) hospital (depending on each site the reference hospital will be different).
- 2- In the ER an anamnesis and a complete physical examination, an electrocardiogram, thoracic X-ray, blood test with blood count, basic biochemistry and coagulation will be done.
- 3- In case the clinical evaluation of the patient shows a specific cause not related to the catheter as the source of the symptoms (pharyngitis for example) it will be specifically treated.
- 4- In case the clinical evaluation points out towards a **thrombotic complication** related to the catheter a **CT Angiography with Venous-Phase** should be done. It will allow identifying the thoracic and neck veins. In case this angiography cannot be performed, a **Doppler echocardiography** made by expert staff will be done.
 - a. If the result is **NEGATIVE** and the general condition is good the patient is discharged and will be controlled by phone and treated symptomatically if needed.
 - b. If the result is **POSITIVE** there are two scenarios:
 - i. If the patient **has fever and infection signs** in addition to a proved thrombosis, the catheter should be removed and the patient admitted to the ER. Perform blood cultures, start anticoagulation treatment and broad-spectrum antibiotic therapy:
[Meropenem 1 g/8h I.V. + Linezolid 600 mg/12h I.V. or similar*](#)
If a bacteremia is confirmed an **echocardiogram** should be done to rule out infectious endocarditis.

- ii. If the **CT Angiography** with Venous-Phase **shows thrombosis** shows thrombosis, the patient has no fever and the general condition is good, the catheter will be removed and treatment will be started with:
[Enoxaparin 1 mg/Kg/12h S.C. or 1.5 mg/Kg/24h.](#)
The patient will be discharged and controlled by phone. It will be sent as soon as possible to a Clinical Hematologist who will advise the patient about the long or short-term anticoagulant therapy.
- 5- If there is clinical suspicious of **pulmonary embolism** (dyspnea, O₂ desaturation, tachycardia, syncope) it should be complemented with a **CT Angiography of the Pulmonary Arteries**. A Pulmonary Thromboembolism (PTE) confirmation always needs anticoagulation treatment and admission to the ER (see Section B).
- 6- The appearance of any thromboembolic complication always means the subject is withdrawn from the study.

B) Pulmonary thromboembolism suspicion

- 1- If a subject has a sudden onset of shortness of breath (dyspnea) and/or syncope, tachycardia or flank pain the caregiver will call the Investigator and will go to a nearby Emergency Room (ER) hospital (depending on each site the reference hospital will be different).
- 2- In the ER an anamnesis and a complete physical examination, an electrocardiogram, thoracic X-ray, blood test with blood count, basic biochemistry, coagulation and arterial blood gas will be done.
- 3- In case the clinical evaluation of the patient shows a specific cause not related to the catheter and as the source of the symptoms it will be specifically treated.
- 4- In case the clinical evaluation points out towards a **PTE** related to the catheter a **CT Angiography with Venous-Phase** (allowing the identification of thoracic and neck veins) and also a **CT Angiography of the Pulmonary Arteries** should be done. In case this angiography cannot be performed, a **Doppler echocardiography** made by expert staff will be done. Depending on the results of the tests there are 3 scenarios:
 - a. If both results are **NEGATIVE** it will be reevaluated to look for other causes. If any other causes are found and the patient is in good general condition the patient is discharged and controlled by phone.

GRIFOLS

- b. In case a **PTE is diagnosed**, the patient should be admitted to the ER and the catheter removed. Treatment will be started with:
Sodium Heparin or low-molecular-weight heparin.
When the subject is discharged it should follow low-molecular-weight heparin or oral anticoagulation therapy and visit a Clinical Hematologist.
 - c. In case a **venous thrombosis (but not a PTE)** is diagnosed the subject will be treated as a PTE: the catheter will be removed and the patient admitted to the ER. Anticoagulation treatment will be started. A Pulmonary ventilation/perfusion scan will be done because a diagnose of PTE is highly probable.
- 5- The appearance of any thromboembolic complication always means the subject is withdrawn from the study.
- 6- The catheter will be always removed except in case of an intra-auricular thrombus. If it is suspected, an **Echocardiogram** should be done to rule it out. It is a highly infrequent complication but potentially severe. The best management of this situation is unclear but could require urgent cardiac surgery.
In this situation anticoagulation treatment with sodium heparin will be started. The catheter will not be removed due to the high risk of embolism and the subject will be urgently sent to a hospital where cardiac surgery can be assessed.

* The antibiotic protocol is a recommendation. You can follow other protocols taking into account that:

- We should include treatment for all skin bacteria usually involved in cutaneous infections.
- We should also include treatment for anaerobic bacteria.
- The catheter of these patients are manipulated weekly, therefore we should include treatment for nosocomial bacteria.

Meropenem is recommended because it is a carbapenem and includes a high number of gram negative, anaerobic and nosocomial bacteria coverage.

To include the rest of the gram positive bacteria coverage, Linezolid is recommended because it is easier to handle than vancomycin.

Meropenem's adverse events are: diarrhea, gastrointestinal discomfort and transaminase increase. Regarding Linezolid the most frequent adverse events are: cutaneous rash, diarrhea and gastrointestinal discomfort and in rare occasion thrombocytopenia.

Bibliography

Bambauer, R. et al., 2012. Surface-Treated versus Untreated Large-Bore Catheters as Vascular Access in Hemodialysis and Apheresis Treatments. *International journal of nephrology*, 2012, p.956136.

Available at:

<http://www.pubmedcentral.nih.gov/articlerender.fcgi?artid=3332189&tool=pmcentrez&rendertype=abstract> [Accessed February 7, 2013].

Burns, K. & McLaren, A., 2009. Catheter-related right atrial thrombus and pulmonary embolism: A case report and systematic review of the literature. *Journal of the Canadian Thoracic*, 16(5), pp.163–165.

Available at: <http://www.ncbi.nlm.nih.gov/pmc/articles/PMC2779172/> [Accessed February 7, 2013].

Debourdeau, P. et al., 2013. International clinical practice guidelines for the treatment and prophylaxis of thrombosis associated with central venous catheters in patients with cancer. *Journal of thrombosis and haemostasis : JTH*, 11(1), pp.71–80.

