4.4 Withdrawal Criteria and Planned Analyses of Withdrawals and Dropouts

The subject will be withdrawn from the study if:

- Prior to the first plasma exchange session, no plasma sample has been collected for possible future assays.
- Any serious adverse event is recorded, advising removal of the subject.
- The subject or his/her legal representative wishes to abandon the study and continue follow-up and normal treatment in the center.
- The investigator is of the opinion that treatment continuation is contraindicated.
- The subject fails to adhere to the study protocol.

The reason for withdrawal of the subject will be documented, and a final visit will be scheduled to obtain blood samples and to complete the pertinent tests. Whenever possible, these tests will be made on the same day as the final visit. No subject can be re-enrolled into the study after having been withdrawn from the study.

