6.2.3 Weeks 7 to 8 – Intermediate visit (Window range +/- 2 days)

Plasma samples will be collected from the subjects (control and full plasma exchange group) to allow the pertinent tests. Additional plasma samples will be collected each time for storage at -70°C and possible future assays.

The following tests will be made: biomarkers of AD (A β -40, A β -42, β -secretase, γ -secretase, cholesterol, LDL, HDL, VLDL, and C-reactive protein, rheumatoid factor, IL-1b, IL-6, ferritin, TNF- α) and plasma IgG.

During the visit medical history will be checked with the recording of any anomalies. Concomitant medication is also to be registered, together with any adverse event detected since the last visit or since the last plasma exchange session.

Central catheter will be also extracted during this intermediate visit.

After the intensive plasma exchange period (weeks 1 to 6) and before Maintenance period, lumbar puncture will be performed to assess the levels of A β -40, A β -42, P-tau, T-tau and other Alzheimer's disease biomarkers together with standard tests (cell counts, glucose, proteins and albumin). Time collection for the CSF must be between 8am and 12am.

During this intermediate visit (weeks 7 to 8) the following cognitive impairment and behavioral tests will be made: ADAS-Cog, MMSE, NPS battery, ADCS-ADL, NPI, CDR-Sb, ADCS-CGIC, CSDD and CSSRS. Likewise, anxiety and restlessness tests will be made based on the Overt Aggression Scale (OAS) and the Agitated Behavior Scale (ABS), if considered opportune.

During the study period between week 7 and 8, a FDG-PET and an MRI will be also carried out.

Control group

The control group will undergo simulated (sham) central catheter removal and will follow the same schedule of assessments as the treated groups

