In case the final visit is conducted before completing the study, some assessments could be avoided. It will be decided case by case and depending on when the last assessments have been done.

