| < 110 lbs | Adjusted Volume [†] | 160 ml | 80 ml | + | 350 ml |
| 110-149 lbs | 690 ml | 160 ml | 80 ml | + | 350 ml |
| 150-174 lbs | 825 ml | 190 ml | 95 ml | + | 400 ml |
| 175-999 lbs | 880 ml | 200 ml | 100 ml | + | 500 ml |

[†]: Plasma volume to collect (ml) = (Patient weight in lbs X 690 ml) / 110 lbs

These procedures are not listed in the protocol and they are recommended to be performed at the discretion of the Investigators and Plasmapheresis Teams.

Finally, as in regular apheresis practice, it is recommended that patients be placed in Trendelenburg position for ALL LVPE procedures.

Signature: _____
 Name of Person: _____
 Job title: _____

Signature: _____
 Name of Person: _____
 Job title: _____

Signature: _____
 Name of Person: _____
 Job title: _____

APPENDIX 11

FEVER MANAGEMENT GUIDELINE

Guideline to manage fever during full plasma exchange (FPE) period in patients with a central line

- 1- Upon the detection of fever, the patient or the caregiver will call the Investigator and will go to a nearby Emergency Room (ER) hospital (depending on each site the reference hospital will be different).
- 2- In the ER an anamnesis and a complete physical examination will be done focused on investigating any potential infection focus. As a routine, an electrocardiogram, thoracic X-ray, blood test with blood count, basic biochemistry and acute phase reactants, urine analysis and urine culture should be done.
- 3- In case patient's temperature is higher than 37.5°C (99.5°F) blood culture from the central line and peripheral blood will be collected. The microbiologist should be asked to inform as quick as possible about any microorganism growth from both, the peripheral and central samples, and the time difference, if any, between both.
- 4- With the information obtained during the anamnesis, the physical examination and the additional tests done in the ER, 3 situations can be considered:
 - a. There are infection signs of soft tissues in the **catheter insertion area but no other apparent infectious foci**: In this case the intervention will be according to the following systemic involvement grade:
 - i. **If there are no clinical or analytical data of systemic involvement** the patient can be discharged and **the cutaneous infection** can be treated empirically with amoxicillin and clavulanic acid at a dose of: **875/125mg 3 times per day during one week**.

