A different antibiotic active against the main microorganisms responsible of cutaneous around-catheter bacterial infections can be used. The Investigator will contact the patient by phone frequently. The patient will

be given a Temperature Log Form which will be completed by the caregiver.

- ii. **If there is high fever (>38°C, >100°F) and systemic involvement** (unconsciousness, tachycardia, hypotension) the patient should be admitted to the hospital. The catheter should be removed and the patient will be treated with a broad-spectrum empiric antibiotic while waiting the culture results. The treatment regimen should cover the most frequent bacteria related to catheter infections; for example, Meropenem (ultra-broad-spectrum injectable antibiotic).

Meropenem 1g I.V. every 8 hours + linezolid 600mg I.V. every 12 hours*

Afterwards the treatment will be according to the antibiogram results. The catheter removal involves subject's study withdrawn.

- b. There is the existence of **clinical and analytical data of an infectious focus other than the catheter:** An UTI (urinary tract infection), a respiratory infection or other infectious focus is diagnosed. In this case the patient will be treated according to the involvement grade:

- i. **If the patient is in good general condition**, does not have high fever, there is no unconsciousness, and the infection can be treated out of the hospital in safe conditions, patient can be discharge with an empiric antibiotic treatment. It is mandatory to daily follow the patient by phone and to be in contact with the microbiologist, who will inform about the culture results. If after 48-72 hours the patient condition has improved, the patient should continue with the treatment regimen; if there is no improvement or there is a worsening of the patient condition, it should go again to the reference ER hospital to get a reevaluation.
- ii. **If the patient is in bad general condition**, has high fever, hemodynamic effects, unconsciousness or the infection is severe (for example, pneumonia), the patient should be admitted to the hospital and be treated. Treatment with empiric antibiotics is started while waiting the culture results.

- c. The patient has fever and there is **not clinical or analytical data that suggest a different infectious focus other than the catheter:** In this case the patient always should be admitted to the hospital and remain under observation.

There are 2 possible scenarios:

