- i. **If the patient is in good general condition** the treatment can wait until the culture results are obtained. A negative blood and catheter culture

results, rules out a catheter infection as a focus. If the good general condition remains the patient could be discharged and be controlled by phone. If the blood and catheter culture results are positive the catheter should be removed and the bacterial infection should be treated.

In any case, both situations require patient's admission until the culture results are obtained.

If the removal of the catheter is required, this involves subject's study withdrawn.

- ii. **If the patient is in bad general condition**, even if there is no local infection around the catheter's insertion point; the catheter should be removed and broad-spectrum antibiotic therapy should be started.

The recommended treatment is:

Meropenem 1g I.V. every 8 hours + linezolid 600mg I.V. every 12 hours*

while waiting the culture results.

The catheter removal involves subject's study withdrawn.

* The antibiotic protocol is a recommendation. You can follow other protocols taking into account that:

- We should include treatment for all skin bacteria usually involved in cutaneous infections.
- We should also include treatment for anaerobic bacteria.
- The catheter of these patients are manipulated weekly, therefore we should include treatment for nosocomial bacteria.

Meropenem is recommended because it is a carbapenem and includes a high number of gram negative, anaerobic and nosocomial bacteria coverage.

To include the rest of the gram positive bacteria coverage, Linezolid is recommended because it is easier to handle than vancomycin.

Meropenem's adverse events are: diarrhea, gastrointestinal discomfort and transaminase increase. Regarding Linezolid the most frequent adverse events are: cutaneous rash, diarrhea and gastrointestinal discomfort and in rare occasion thrombocytopenia.

Bibliography

Bambauer, R. et al., 2012. Surface-Treated versus Untreated Large-Bore Catheters as Vascular Access in Hemodialysis and Apheresis Treatments. *International journal of nephrology*, 2012, p.956136.

Available at:

<http://www.pubmedcentral.nih.gov/articlerender.fcgi?artid=3332189&tool=pmcentrez&rendertype=abstract> [Accessed February 7, 2013].

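### Stopping treatment for catheter removal or thromboembolism also ends follow-up, so Month 14 co-primary scores are lost avoidably, and the catheter-related part falls only on the active arms

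*Protocol*

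**What the plan says.** Protocol section 4.4 lists reasons for withdrawal from the study. They include a serious adverse event that advises removal and the investigator's opinion that further treatment is contraindicated. For a withdrawn subject, "a final visit will be scheduled to obtain blood samples and to complete the pertinent tests". Re-enrolment is excluded and no later assessment is described. Section 6.2.5 adds: "In case the final visit is conducted before completing the study, some assessments could be avoided". That choice is made case by case, depending on when the last assessments took place.

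Appendix 11 is headed "Guideline to manage fever during full plasma exchange (FPE) period in patients with a central line". It links removal of the line to leaving the study in three branches:
- 4.a.ii, catheter-site infection with high fever and systemic involvement: "The catheter removal involves subject's study withdrawn".
- 4.c.i, fever without another focus and positive cultures: "If the removal of the catheter is required, this involves subject's study withdrawn".
- 4.c.ii, fever without another focus in a patient in bad general condition: "even if there is no local infection around the catheter's insertion point; the catheter should be removed", with cultures still pending and the same withdrawal consequence.

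Appendix 12 covers thromboembolism in the same period and says in A item 6, and again in B item 5: "The appearance of any thromboembolic complication always means the subject is withdrawn from the study".

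In the SAP, section 5.1 keeps in the FAS any active-arm patient who had at least one exchange. Section 7 assigns efficacy assessments to visits by study day. Section 8 does not impute missing values. Section 9.1.1 fits an MMRM to Months 2, 6, 9, 12 and 14, with Month 14 primary.

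**The concern.** Thrombosis or line sepsis is a good reason to stop exchanges. It is no reason to stop asking for ADAS-Cog and ADCS-ADL. Because the protocol ties the two together, some Month 14 scores go missing for a reason that the treatment procedure itself causes.

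The catheter-related part cannot occur in the control arm, so it adds to dropout on one side only, whereas the 15% dropout assumption is a single global figure. Once the scores have not been collected, no analysis can bring them back. What is at stake is the comparability of the FAS arms at Month 14 on both co-primary endpoints.

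**Working it through.** **1. What happens to one patient's data.**
- With weekly exchanges from day 1, the sixth is on day 1 + 5 × 7 = 36. An early final visit in or soon after this period falls in the SAP section 7 window for the Intermediate visit, days 2 to 93. The Final Visit window starts at day 344.
- The patient stays in the FAS, gives the MMRM at most a Month 2 score, and has no Month 6, 9, 12 or 14 score.

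**2. Which arms are exposed.**
- Protocol section 3.4 calls the control procedure non-invasive. Appendix 9 (1.1.2) fixes the cut sham catheter to a skin patch, so no vein is entered.
- Appendix 11 applies to patients with a central line. Section 5.1.3 allows peripheral or central access. Catheter-related withdrawal can therefore arise only in active-arm patients with central access.
- The Appendix 12 rule covers any thromboembolic complication, so an event unrelated to a catheter could also remove a sham patient.

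**3. The plan's own power (section 4.3).** Inputs: 78 evaluable per arm, two-sided 5%; ADAS-Cog difference 3, SD 5.55; ADCS-ADL difference 6.69, SD 10.0. Normal approximation: power = Φ(δ / [SD × √(1/n₁ + 1/n₂)] − 1.96).
- ADAS-Cog: 3 / (5.55 × √(2/78)) = 3.376; Φ(1.416) = 92.2%.
- ADCS-ADL: 6.69 / (10 × √(2/78)) = 4.178; Φ(2.218) = 98.7%.
- Joint: 0.922 × 0.987 = 0.91. The stated 92%, 98% and 90% are reproduced.

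**4. Number affected.** Enrolled per arm 364/4 = 91; evaluable 312/4 = 78; dropout allowance 91 − 78 = 13 per arm. Section 5.2.2.5 puts infections below 3% of all catheters. Taking every active patient as having central access and every infection as leading to removal:
- per active arm, 0.03 × 91 = 2.7, so under about 3;
- three active arms, 0.03 × 273 = 8.2, so under about 8;
- sham, 0 from the catheter rules.

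**5. Power if 3 patients are lost on top of the 13.** Active 75, sham 78:
- ADAS-Cog: 3 / (5.55 × √(1/78 + 1/75)) = 3.342; Φ(1.382) = 91.7%.
- ADCS-ADL: 98.5%.
- Joint: 0.917 × 0.985 = 0.903, still above the stated 90%.

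If the 3 fall within the 13, planned power does not change.

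**6. What the planned checks can do.** The LOCF ANCOVA carries forward an early score if there is one. The complete-case ANCOVA drops the patient. The random slope model extrapolates from early data. The comparison of completers with drop-outs is descriptive. All reuse scores already collected; none supplies Months 6 to 14.

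**The case against.** **The guidelines are only advice.** Section 5.2.2.5 calls them recommendations and tells sites to follow local procedures, and Appendix 11's wording is softer than the *always* of Appendix 12. This stands in part, since a site could act otherwise. But section 11 makes attached documents part of the protocol, and section 4.4 leads to the same result.

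**The appendices are not the root.** Many of these patients would be withdrawn under section 4.4 anyway. This stands: the general cause is that 4.4 has no off-treatment follow-up, and the appendices are specific applications of it.

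**The early visit is not a licence to skip scales.** Also correct, because omissions depend on how recent the last assessments are. Yet even a complete early visit yields only a Month 2 score.

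**The number is small.** At the documented bound it is, and it may lie within the dropout allowance.

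Three stronger readings are tempting and are not supported:
- Section 5.2.2.5 also gives fewer than 5 infections per 1000 days, and section 6.2.3 says "Central catheter will be also extracted during this intermediate visit". A reader might multiply: 1 − exp(−0.005 × 42) = 18.9% and 1 − exp(−0.005 × 56) = 24.4%, or about 17 to 22 per active arm, above the allowance of 13. But both figures are upper bounds in one sentence. Both hold at any rate below −ln(0.97)/56 to −ln(0.97)/42, about 0.54 to 0.73 per 1000 days. The 19% to 24% case treats the looser bound as a rate and contradicts the 3% bound beside it. The same sentence says subclavian lines are infected less often, and Appendix 11 (4.a.i) treats local infection without removal.
- A reader might turn the loss into a shift in the ADAS-Cog mean. That needs a difference between missing and retained patients, and the documents give none.
- A reader might take the SAP section 9.1.1 remark on non-random drop-out as an admission about these patients. It concerns patients who benefit less from treatment, which is a different mechanism.

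**Conclusion.** The point holds as a retention and missing-data issue. The plan creates avoidable missing Month 14 scores on both co-primaries, caused by the treatment procedure. The catheter-related part falls only on the active arms, and the planned analyses cannot recover the scores.

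The documented size is small: under about 3 of 91 per active arm and half a percentage point of ADAS-Cog power at worst. That count assumes central access for everyone and removal for every infection, both of which overstate it. It leaves out removals under 4.c.ii without proven infection and all thromboembolic events, for which the documents give no rate, so the total is uncertain. The documents do not establish the direction or size of any bias. This is a low-cost improvement worth making, not a threat to the trial's power.

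**What to change.** In protocol section 4.4, Appendix 11 (4.a.ii, 4.c.i, 4.c.ii) and Appendix 12 (A6, B5), replace study withdrawal with: *Study treatment is discontinued; unless consent is withdrawn, the subject continues the scheduled ADAS-Cog and ADCS-ADL assessments at Months 6, 9, 12 and 14.*

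In SAP section 9.2.1, state that these scores enter the FAS MMRM. Add a sensitivity MMRM that excludes scores collected after treatment discontinuation. The visit slotting needs no change: SAP section 7 already counts from the first full exchange whatever the treatment deviations.

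The cost is amendment wording plus up to four exchange-free visits per affected patient, about 8 × 4 = 32 over the three active arms at the 3% bound, with an uncounted number for the other cases. Some retained scores will be off treatment, so the primary estimate moves toward a treatment-policy effect and may be slightly diluted. The change does not help where consent is withdrawn or the visit dates have already passed.
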